1.0 Research Design

1.1 Purpose/Specific Aims

To test the extent to which tailored outreach text messages that provide a cue to action and an intervention that enhances access to poverty-reducing resources, in combination with a primary care literacy promotion program, can improve parenting behaviors, child language development, and social-emotional skill acquisition among low-income Latino children.

A. Objectives

Aim 1: To test the relative efficacy of 3 literacy promotion interventions on parenting behaviors, child language and social emotional skill acquisition among low-income Latino children

Aim 2: To examine mechanisms underlying the effects of the interventions

Aim 3: To conduct a mixed methods process evaluation of the literacy promotion interventions

Research question (RQ) 1: How are the literacy promotion interventions implemented?

RQ 2: What are barriers, facilitators, and modifications made to the interventions?

RQ 3: What are parents' experiences with the interventions?

B. Hypotheses / Research Question(s)

Hypotheses (H) 1A: Children in the ROR + texts arm will have enhanced language and social-emotional skill acquisition, and parents will describe enhanced parenting behavior, as compared to those receiving ROR only

H1B: Children in the ROR + texts + Connecting NJ (formerly Central Intake) arm will have enhanced language and social-emotional skill acquisition, and parents will describe enhanced parenting behavior, as compared to those receiving ROR only or ROR + texts

H2A: Effects of the interventions on child language and social-emotional outcomes will be partially mediated by the home literacy environment.

H2B: The effect of ROR + texts + Connecting NJ child outcomes will be partially mediated by reduction in parent stress and aspects of positive parenting (responsive verbal interactions)

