6.0 Data Management Plan

6.1 Data Analysis

1. Enrollment: We will recruit 630 parent-child dyads (210 per arm) over a 24-month time period. We expect that 80% of the 630 enrolled parent-child dyads will complete the study, leaving 525 parent-child dyads (175 in each arm).

2. Sample size and power:

630 parent-child dyads (210 per arm) will be sufficient to achieve 80% power to detect a 0.3 standard deviation (SD) difference in the primary endpoints language scores on the EOWPVT-4 and social-emotional skill scores on the DECA at 18 months between (1) ROR + texts and ROR only and (2) ROR + texts + Central Intake and ROR + texts, assuming approximately 20% attrition based on our past work²⁹ and using 0.05 significance level. An effect size of 0.3 SD difference would be clinically meaningful since it would be associated with a detectable difference in later cognitive functioning, based on work from a prospective cohort.³⁰ The proposed sample size will provide 99.9% power to detect a 0.6 SD difference between the community resource arm and ROR only, based on the expected additive effects of the text message and enhanced access to poverty-reducing resources.

3. Analysis:

Distributions of baseline characteristics will be summarized overall as well as by randomization group. We will assess the distribution of outcome data using descriptive statistics to check the assumption of normality for continuous variables. We will estimate mean outcomes for each treatment group as well as mean differences between groups (with confidence intervals). If any continuous outcomes are skewed, we attempt log-transformation or other to stabilize the variance and normalize distributions.

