For the mediation analyses in Aim 2, we will examine the extent to which the home literacy environment mediates the effect of the interventions on language skill and social-emotional skill acquisition using the product of coefficients method with each outcome at each post-intervention timepoint individually.³² We will calculate bootstrap bias-corrected confidence intervals ($n=5,000$) to estimate the proportion of treatment effect explained via the home literacy environment. While we expect the effect of the ROR + text messages (arm 2) intervention will mainly operate through the home literacy environment (parent investment) based on our conceptual framework, we expect that the ROR + text + Connecting NJ (arm 3) intervention will also have effects on parenting stress and other responsive parenting interactions (parental verbal responsiveness) through increased access to poverty-reducing community resources accounting for the greater hypothesized impact. We will test this more complex conceptual framework based on an adaptation of the Gershoff model using Structural Equation modeling without latent factors.

For aim 3, the mixed methods approach will allow us to systematically compare data on intervention implementation with the perspectives of parents and clinicians in an ongoing manner. Integration of quantitative and qualitative data will occur at the design, methods, and reporting levels. We will use a convergent design in which we collect quantitative data on key intervention components in the same time frame as we conduct observation (if possible) of study visits.

Parent-child observations will be analyzed by the study team, led by [name]. The observations will be coded according to parent-child interactive behaviors (did expected behaviors occur or not).

Practice and clinician surveys and clinician interviews will be analyzed using qualitative methods to identify changes and adaptations to ROR implementation protocols over time. The evaluation aims to determine what was implemented, how it was implemented, and what changes occurred to implementation over time. We also seek to understand how clinic context affected implementation. These qualitative findings will help inform our quantitative patient-reported outcomes.

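### The only interval planned for H2A is on the proportion mediated, which says little about how much is mediated at the 0.3 SD effect the trial is sized for

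*Combined protocol and SAP*

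**What the plan says.** H2A (section 1.1) predicts partial mediation: "Effects of the interventions on child language and social-emotional outcomes will be partially mediated by the home literacy environment". The analysis is in the Aim 2 paragraph of section 6.1, Data Analysis. It is to be done "using the product of coefficients method with each outcome at each post-intervention timepoint individually". The next sentence gives the inference: "We will calculate bootstrap bias-corrected confidence intervals", with 5,000 draws, "to estimate the proportion of treatment effect explained via the home literacy environment".

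That is the only interval named for the home-literacy mediation. The section gives no interval or test for the indirect effect, no condition that a total effect be established before the ratio is formed, no rule for ratios below 0 or above 1, and no precision statement for Aim 2. The stress and verbal-responsiveness paths of H2B are assigned separately to a structural equation model.

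The planning figures are in the sample-size part of the same section. The enrolled sample "will be sufficient to achieve 80% power to detect a 0.3 standard deviation (SD) difference in the primary endpoints language scores on the EOWPVT-4" and on the DECA for each adjacent-arm contrast, and it gives "99.9% power to detect a 0.6 SD difference between the community resource arm and ROR only". The plan counts on 175 analysable dyads per arm. A literal 20% loss from 210 would leave 168, so both are used below.

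**The concern.** The product of coefficients gives an indirect effect a×b, where a is the effect of treatment on the mediator and b is the effect of the mediator on the outcome given treatment. The proportion mediated is a×b/c, with c the total effect. A ratio is estimated well only when its denominator is many standard errors from zero. A trial sized for 80% power puts the denominator less than 3 standard errors from zero at its own design effect, so the ratio inherits a long upper tail whatever the state of the numerator.

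What is at stake is the size of the mediated share. H2A claims partial mediation. An interval running from below 0.2 to above 1 does not distinguish a minor, a partial and a complete mediating role. The analysis is repeated for each outcome and timepoint, so any outcome with a total effect below 0.3 SD fares worse. If the indirect effect is not pre-specified as the inferential quantity, the choice between it and the ratio can also be made after the results are seen.

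**Working it through.** **Inputs.** From section 6.1: c = 0.3 SD (adjacent arms) or 0.6 SD (arm 3 versus arm 1), alpha 0.05 (taken as two-sided), 175 per arm (168 as a variant). Not in the documents, so assumed: a = 0.2 to 0.5 SD, true proportion 0.3 to 0.7, b = c × proportion / a, within-arm SD 1 for mediator and outcome.

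**1. The plan's own figure.** SE(c) = √(2/175) = 0.107. c/SE = 0.3/0.107 = 2.81. Power = Φ(2.81 − 1.96) = 80.1%, which reproduces the stated 80% (78.5% at 168 per arm). At 0.6 SD the power is 99.99%, consistent with the stated 99.9%.

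**2. The denominator.** 95% interval for c: 0.3 ± 1.96 × 0.107 = 0.09 to 0.51 SD. The denominator alone varies more than fivefold. This needs no assumption about the mediator.

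**3. Hand check of the ratio (Fieller), with a = 0.4, b = 0.375, true proportion 0.5.**
- Var(a) = Var(c) = 2/175 = 0.011429
- Var(b) = (1 − 0.375²)/350 = 0.002455
- Var(ab) = a²Var(b) + b²Var(a) = 0.000393 + 0.001607 = 0.002000
- Cov(ab, c) = b² × 2/175 = 0.001607

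The limits r solve (0.15 − 0.3r)² = 1.96² × (0.002000 − 2 × 0.001607r + 0.011429r²), that is 0.0461r² − 0.0777r + 0.0148 = 0. So r = 0.22 and 1.47.

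For the indirect effect, 0.15 ± 1.96 × √0.002000 = 0.06 to 0.24 SD, which is clear of zero.

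**4. The same check at 0.6 SD, with a = 0.4, b = 0.75.** Var(b) = 0.00125, Var(ab) = 0.006629, Cov = 0.006429. The equation is 0.3161r² − 0.3106r + 0.0645 = 0, so r = 0.30 and 0.68. The ratio is usable here.

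**5. Simulation of the planned method.** Bias-corrected bootstrap for both quantities, c = 0.3, 175 per arm, 300 trials × 1,500 draws:

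| a | True proportion | Median interval for proportion | Upper limit > 1 | Lower limit > 0 | Indirect effect excludes 0 |
|---|---|---|---|---|---|
| 0.2 | 0.3 | −0.02 to 0.81 | 38% | 46% | 51% |
| 0.3 | 0.3 | 0.06 to 1.00 | 50% | 67% | 81% |
| 0.3 | 0.5 | 0.14 to 1.20 | 61% | 70% | 79% |
| 0.4 | 0.5 | 0.19 to 1.40 | 65% | 89% | 97% |
| 0.5 | 0.3 | 0.07 to 0.91 | 46% | 79% | 92% |
| 0.5 | 0.5 | 0.20 to 1.55 | 71% | 89% | 99% |
| 0.5 | 0.7 | 0.32 to 1.98 | 86% | 87% | 100% |

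A separate run at 168 to 175 per arm, with a = 0.3 to 0.4 and proportion 0.3 to 0.5, gave median width 0.8 to 1.2, 90th-percentile width 7 to 18, and intervals outside 0 to 1 in 53% to 72% of trials. The lower limit exceeded 0 in 67% to 88%, and the indirect effect excluded zero in 76% to 97%.

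**6. Sensitivity (a = 0.4, true proportion 0.5).** Median interval with 5,000 draws: 0.19 to 1.43. With 168 per arm: 0.19 to 1.35. With an effective 233 per arm (assumed baseline correlation 0.5): 0.24 to 1.09. Restricted to trials with a significant total effect: 0.20 to 1.17. At c = 0.6: 0.31 to 0.68 (0.29 to 0.68 in the separate run).

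**The case against.** **An indirect-effect interval may already be intended.** Section 6.1 names the product of coefficients and cites a methods paper on resampling for indirect effects. That is a fair hint. But the only interval written down is for the proportion, and the plan should say which quantity carries the inference.

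**The planned interval does not leave Aim 2 unanswered.** A reader might infer that it does. In the settings above its lower limit usually exceeds zero once a is 0.3 SD or more, so it often shows that mediation exists. An upper limit above 1 means only that complete mediation is not excluded. The loss is in efficiency and in the size of the share.

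**The ratio is not inestimable with this sample.** At 0.6 SD, which the plan expects for arm 3 versus arm 1, it is tolerably precise. Nor are wrong-sign denominators common at 0.3 SD: they average 2% to 3% of draws. That is enough to damage the tail that sets the limit, but not enough to make every interval useless.

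**H2B is not affected.** The sentence at issue concerns only the home literacy environment.

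**The indirect effect alone does not settle partial mediation.** This stands, and it shapes the fix. Separating partial from complete mediation also needs the direct or total effect. At 0.3 SD the indirect and direct effects both exclude zero in only 27% to 40% of trials. Part of the limitation is sample size, which no choice of summary removes.

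**The widths are in different units.** Dividing the step 3 indirect-effect width by 0.3 gives (0.238 − 0.062)/0.3 = 0.59, against 1.47 − 0.22 = 1.25 for the ratio. The gain is roughly twofold, and that comparison treats c as known.

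**Conclusion.** The point holds for H2A at the adjacent-arm contrasts. The stated inferential quantity is a ratio whose 95% interval, at the trial's own 0.3 SD effect, typically spans most of the 0 to 1 scale or more, while a more efficient quantity comes from the same draws.

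The imprecision of the denominator follows from the design power alone. The widths and detection rates rest on assumed mediator paths. The direction held across every path tried at 0.3 SD, but the advantage is small when the mediator effect is weak (51% against 46% at a = 0.2).

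The documents do not support extending this to arm 3 versus arm 1 at 0.6 SD, to H2B, or to a claim that mediation would go undetected. It is a worthwhile change to a mechanistic aim and does not bear on the primary treatment comparisons.

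**What to change.** In the Aim 2 paragraph of section 6.1:

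- Make the indirect effect (product of coefficients, in outcome SD units) with its 5,000-draw bootstrap interval the H2A estimate and test, for each arm contrast, outcome and timepoint.
- Report the direct and total effects with intervals beside it, so that a claim of partial mediation can be judged.
- Give the proportion mediated as a descriptive secondary figure, only where the total effect is clearly non-zero, and define that condition in advance (for example, its 95% interval excludes zero).

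The cost is a few sentences in the plan and no new data, since the bootstrap already produces the quantities. The percentage mediated loses its headline place, and partial versus complete mediation will remain imprecise at 0.3 SD. The plan should say so.

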6.2 Data Security

The study team will employ several measures to secure data. Only trained study team members supervised by the PI will have contact with participants and access to the study data. ALL participants (parent-child pairs, practice administrators, and practice clinicians) will receive a unique code number and names will not appear on data. The key list linking participant identification with numeric codes will be locked in a secure filing cabinet or digital folder and the key will be destroyed when data analysis is complete. All data will be stored on password protected computers or REDCap or a secure server/restricted folder. When possible, parent survey information will be directly entered into REDCap. Practice administrator and clinician survey data will be entered into Qualtrics and downloaded into a document and saved in a restricted folder on a secure drive. Interview recordings and transcripts and other documents from the interviews (notes, process maps) will also be saved on this folder. The research study data will be stored for 6 years after the study completion. Video recordings of the parent-child interactions will be deleted after they are coded in REDCap.

6.3 Data and Safety Monitoring

A. Data/Safety Monitoring Plan

1. Overall framework for safety monitoring and information to be monitored: The principal investigator (PI) and study team will implement a data and safety monitoring plan. The proposed clinical trial presents minimal risk to participants. For the proposed study, we will utilize standard Rutgers procedures and infrastructure for data and safety monitoring. All study team members have completed

or will complete certification in the protection of research participants before the beginning of the study. We will monitor quality assurance and participant confidentiality throughout the study as well as adverse events. We will also convene a Data Safety and Monitoring Board (DSMB) to ensure the safety of our study participants. The specific elements of our plan are described below. We have an NIH Certificate of Confidentiality, which will be issued automatically, and we have included this language in our consent forms.

2. Frequency of monitoring: We will implement specific monitoring procedures at regular intervals concerning quality assurance and participant confidentiality. We describe procedures for monitoring and reporting of adverse events further below on this page.

a. Weekly team meetings: We will utilize weekly team meetings to monitor quality assurance and confidentiality procedures. All participants will be screened for eligibility using a checklist created for this study and the PI will audit accrual to ensure that participants meet eligibility criteria. In addition, the PI will regularly audit the study files to ensure that questionnaires and assessments completed by participants contain all study items. In order to protect confidentiality all data will be numerically coded and information linking the numeric codes to the participant's name will be kept in separate secured files (e.g., cabinet in a secured office or secure research drive). In addition, computer data files will be stored on password-protected computers and communication among study staff will use participant code numbers, not names or other identifiers.

b. Annual and interim IRB monitoring: After initial approval, the protocol will be subject to annual review by the RBHS IRB to ensure adherence to the scientific and ethical aspects of the proposal.

3. Adverse event monitoring and reporting: We will implement a specific set of procedures concerning the reporting of adverse events as outlined below.

a. Regular and repeated assessment of adverse events: While unlikely, any adverse events from the study's literacy promotion interventions will be closely monitored and assessed throughout the duration of the project. Opportunities to do so include the ongoing process evaluation and participant follow-up visits. These contacts will be made in-person or by telephone by trained study team members.

b. Regular and repeated reporting of adverse events: All adverse events and unanticipated problems will be reported to the PI upon discovery. All reported adverse events will be reported to the IRB and DSMB (see below) within 48 hours of discovery; all such events will be reported to study co-investigators and staff and to NIH within 72 hours of discovery. Adverse events will also be discussed at weekly meetings between the PI and study team.

B. Data/Safety Monitoring Board Details

A data and safety monitoring board (DSMB) will be used for this study. The specific aspects of the DSMB for this study are as follows:

a. The DSMB will consist of 3 members: a physician-scientist from Rutgers Robert Wood Johnson Medical School who will serve as DSMB Chair; a biostatistician from the Rutgers School of Public Health; and a behavioral scientist from Rutgers Robert Wood Johnson Medical School. All members will have expertise in guidelines and policies concerning the protection of research participants.

b. The DSMB will meet twice per year to review study data concerning recruitment, randomization, retention, compliance, form completion, inclusion, intervention effects, and safety. In addition, the DSMB will: (1) identify specific safety concerns for participants and communicate these to the study PI; (2) consider the need for additional data concerning participant safety; (3) consider the rationale for the continuation of the study; (4) provide a written report concerning the protocol to the IRB and study PIs; and (5) review manuscripts reporting study results prior to submission.

c. Any safety concerns will result in suspension of the study however given the nature of the interventions and that study risks are not greater than minimal the probability of this occurring is very low.

6.4 Reporting Results

A. Individual Subjects' Results

Study participants will not receive survey assessments, but RAs will discuss the intent, use, and meaning of the surveys with participants in more detail than when originally describing the study if asked.

B. Aggregate Results

Aggregate results will be shared with health center leadership and their community board as well as through community presentations including our community advisory board.

C. Professional Reporting

Research findings will be shared with the scientific community through preparation of a manuscript.

D. Clinical Trials Registration, Results Reporting and Consent Posting

We will register the trial through ClinicalTrials.org and comply with reporting requirements required for this study.

6.5 Secondary Use of the Data

As required by the NIH data sharing policy, the principal investigator will respond to bona fide requests from researchers for de-identified data as follows:

1) Research resources and information developed in this project will be made available to the scientific community for non-profit research purposes in accordance with and where required by relevant NIH Grants Policy Statement and the Principles and Guidelines for Recipients of NIH Research Grants and Contracts.

2) Data sharing plan: The data sharing plan for the proposed research is based on the NIH Data Sharing Policy and Implementation Guidance. The proposed research will include longitudinal data from up to 630 parent-child dyads. The final dataset will include parent-reported demographic and behavior data as well as direct assessments of child development. Safeguarding the privacy of participants will be of the highest priority. We will make the data and associated documentation available to users conducting non-profit research only under a written data-sharing agreement. Individuals requesting data under the agreement will commit to (1) using the data only for research purposes and not to identify any individual participant; (2) securing the data using appropriate computer technology; and (3) destroying or returning the data after analyses are completed. The dataset will be stripped of all identifiers prior to sharing.

Only the PI will have access to data that is audio- and/or video-recorded for future research, as these data cannot be rendered fully de-identified.

3) Criteria, mechanisms and timetable: Written request by individuals for information pursuant to non-profit research will be made to [name]. Bona fide requests for information will be provided within a reasonable length of time in accordance with and where required by relevant NIH Grants Policy and the Principles and Guidelines for Recipients of NIH Research Grants and Contracts.

7.0 Research Repositories – Specimens and/or Data

Not applicable

8.0 Approvals/Authorizations

See letters of cooperation from participating CHCs.

